9.1 Enrolled Subjects and Screen Failures

Population: Consented Subjects

Target Phases: Core Phase

Contents:

- Calculate the number of subjects who consented.
- Calculate the number of subjects and the percentages for the following items:

Core Phase

- Subjects who were enrolled
- Subjects of screen failure
- Reasons for screen failure
 - Did not satisfy Inclusion/Exclusion criteria
 - Withdrawal by Subject
 - Other
- Subjects who were treated with study drug/not treated with study drug

Definitions: Enrolled = Consented – Screen failure

For each of the following items, the denominator is defined as noted below
Core Phase

| Items | The denominator of percentage |
|---|----------------------------------|
| 
• Consented• Enrolled• Screen failures• Reasons for screen failure• Not treated• Treated | The number of Consented Subjects |

9.2 Subject Disposition

Population: Safety Set

Target Phases: Core Phase, Extension Phase

Contents: - Calculate the number of subjects and the percentages for the following items:

Core Phase

- Subjects who enrolled into core phase study
- Subjects who completed study/discontinued study
- Reasons for discontinuation of study
 - Withdrawal of Consent
 - Subject Non-Compliance
 - Subject failed to meet inclusion/exclusion criterion
 - Significant Medical Condition
 - Adverse Event
 - Pregnancy
 - Investigator discretion
 - Sponsor request
 - Subject requires prohibited concomitant medication
 - Study terminated
 - Lack of efficacy at the maximum dose level (Level 6)
 - Other
- Subjects who completed treatment/discontinued treatment
- Reasons for discontinuation of treatment
 - Lack of efficacy at the maximum dose level (Level 6)
 - Subjects who require rescue therapy more than 3 times or continuous rescue therapy for more than 3 weeks
 - Excessive platelet count responses ($>400 \times 10^9/L$) at the minimum dose level (Level 1)
 - Treatment with certain ITP therapies/procedures, such as vinca alkaloids, cyclophosphamide, rituximab, splenectomy, or other TPO-RAs (eltrombopag, romiplostim)
 - Other

Extension Phase

- Subjects who entered Extension Phase
- Subjects who were treated with study drug
- Subjects who weren't treated with study drug
- Subjects who completed study/discontinued study
- Reasons for discontinuation of study
 - Withdrawal of Consent
 - Subject Non-Compliance
 - Subject failed to meet inclusion/exclusion criterion
 - Significant Medical Condition
 - Adverse Event

- Pregnancy
- Investigator discretion
- Sponsor request
- Subject requires prohibited concomitant medication
- Study terminated
- Lack of efficacy at the maximum dose level (Level 6)
- Other
- Subjects who are ongoing in the extension phase*
- Subjects who completed treatment/discontinued treatment
- Reasons for discontinuation of treatment
 - Lack of efficacy at the maximum dose level (Level 6)
 - Subjects who require rescue therapy more than 3 times or continuous rescue therapy for more than 3 weeks
 - Excessive platelet count responses ($>400 \times 10^9/L$) at the minimum dose level (Level 1)
 - Treatment with certain ITP therapies/procedures, such as vinca alkaloids, cyclophosphamide, rituximab, splenectomy, or other TPO-RAs (eltrombopag, romiplostim)
 - Other

*: Item “Subjects who are ongoing in the extension phase” only exists in the first analysis (after the last patient completes the Core Phase).

If a subject has multiple discontinuation reasons, they will be counted for each individual discontinuation reason.

Definitions: For each of the following items, the denominator is defined as noted below.
Core Phase

| Items | The denominator of percentage |
|--|--|
| 
 • Enrolled into core phase study • Completed the core phase study • Discontinued the core phase study • Reason for discontinuation • Completed the core phase treatment • Prematurely discontinued the core phase treatment • Reason for discontinuation | The number of subjects in Safety Set of Core Phase |

Extension Phase

| Items | The denominator of percentage |
|--|---|
| 
 • Entered the Extension Phase • Treated with study drug • Not treated with study drug • Completed study • Discontinued the study • Reasons for discontinuation of study | The number of subjects in Safety Set of Extension Phase |

| | |
|---|--|
| 
 • Ongoing in the extension phase • Completed the treatment • Discontinued the treatment • Reasons for discontinuation of treatment | |
|---|--|

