# 5.3.1 Subjects with Study Drug Discontinuation

In both the Primary Investigation Phase (Core Phase) and the Extension Phase, study drug may be permanently discontinued at the discretion of the Investigator due to safety reasons, at the request of the subject, or if any of the following occur:

- Platelet count remains <30×10^9/L after more than 3 weeks at the maximum dose level (Level 6) (subjects can be discontinued after 7 days of therapy at the maximum dose level if they have dangerously low platelet counts in the opinion of the Investigator)
- Subjects who require rescue therapy more than 3 times or continuous rescue therapy for more than 3 weeks
- Excessive platelet count responses (> $400 \times 10^9$ /L) at the minimum dose level (Level 1)
- Treatment with certain ITP therapies/procedures, such as vinca alkaloids, cyclophosphamide, rituximab, splenectomy, or other TPO-RAs (eltrombopag, romiplostim).

If a subject discontinues study drug due to an AE, the Investigator will attempt to follow the event until it has resolved or stabilized.

If possible, a subject who discontinues treatment will complete the EOT assessments for the applicable phase and protocol-specified information will be collected. The primary reason for discontinuation and all other reason(s) contributing to the subject's discontinuation from study drug(s) as well as the date of last dose should be collected in the CRF.

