13.2.1 Overview of Treatment-emergent Adverse Events

Population: Safety Set

Target Phases: Core Phase, Core Phase and Extension Phase

Analysis items: - TEAEs, Related TEAEs, Serious TEAEs, Serious Related TEAEs, TEAEs by maximum severity (Grade 1, Grade 2, Grade 3, Grade 4, Grade 5, Grade ≥ 3), TEAEs of Special Interest (Thromboembolic events, Bleeding events (CTCAE Grades 3 and 4)), Related TEAEs of Special Interest, TEAEs leading to death

Contents: - The number of events and the number and proportion of subjects who experienced at least 1 event in the Analysis items are calculated.

Definitions: - The denominator to calculate the proportion is the target population.

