13.2.3 Treatment-emergent Adverse Events by SOC and PT

Population: Safety Set

Target Phases: Core Phase, Core Phase and Extension Phase

Analysis items: - TEAEs, Related TEAEs, Serious TEAEs, TEAEs leading to death

Contents: - The number and proportion of subjects with the Analysis items are calculated.
- The number and proportion of subjects in case of the other Analysis items are calculated by SOC and PT.

Definitions: - The denominator to calculate the proportion is the target population.

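### SAP 9.2 gives no adverse-event or subject-request reason for stopping treatment, and no summary covers TEAEs leading to discontinuation of study drug

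*SAP*

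**What the plan says.** Protocol 5.3.1 applies to both phases. It opens with two general grounds: "study drug may be permanently discontinued at the discretion of the Investigator due to safety reasons, at the request of the subject". Four specific events follow: persistently low platelets at dose Level 6, repeated or prolonged rescue, excessive response at Level 1, and treatment with certain other ITP therapies or procedures. The section foresees a stop for an adverse event ("If a subject discontinues study drug due to an AE") and requires the primary reason and every contributing reason to be collected in the CRF.

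SAP 9.2 summarises two outcomes in each phase, each with its own reasons. The list headed "Reasons for discontinuation of study" has 12 entries, among them Adverse Event, Withdrawal of Consent, Significant Medical Condition and Investigator discretion. The list headed "Reasons for discontinuation of treatment" has five: the four specific events and Other.

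For adverse events, the overview in SAP 13.2.1 ends with "Related TEAEs of Special Interest, TEAEs leading to death". The SOC and PT summary in SAP 13.2.3 covers "TEAEs, Related TEAEs, Serious TEAEs, TEAEs leading to death".

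The Extension Phase primary objective (Protocol 2.2.1, SAP 3.2.1) concerns the safety and tolerability of long-term treatment. The Core Phase has safety as a secondary objective and does not mention tolerability.

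**The concern.** The SAP carries over the specific stopping events from Protocol 5.3.1 and leaves out the two general grounds placed ahead of them. A subject taken off drug because of an adverse event and a subject who simply asks to stop would both fall under Other, where they cannot be told apart.

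What is at stake is how the tolerability result can be read. Stopping drug because of an adverse event bears directly on tolerability, and tolerability is part of the Extension Phase primary objective. If no summary counts those stops or names the events behind them, the report on that objective has to be pieced together from subject-level data, if the listings allow it.

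**Working it through.** No figure in the plan is in dispute, so this is a comparison of text and a count.

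**Step 1: protocol grounds against the SAP treatment list.**

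| Ground in Protocol 5.3.1 | Row in the SAP 9.2 treatment list (both phases) |
|---|---|
| Safety reasons, at the investigator's discretion | None; falls under Other |
| Subject's request | None; falls under Other |
| Persistently low count at Level 6 | Yes, as lack of efficacy at Level 6 |
| Repeated or prolonged rescue | Yes |
| Excessive response at Level 1 | Yes |
| Certain other ITP therapies or procedures | Yes |

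Six grounds against four specific rows leaves 6 − 4 = 2 without a row. SAP 5.1, which records changes from the protocol's planned analyses, does not mention the omission.

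**Step 2: TEAE outputs.** SAP 13.2.1 to 13.2.8 holds eight summaries: overview, overview by subgroup, SOC and PT, special interest, SOC and PT by subgroup, PT by frequency, maximum severity, and time to onset. Number covering TEAEs that led to stopping study drug: 0 of 8. SAP 14 has three dedicated TEAE listings (leading to death, serious, special interest). Number covering TEAEs that led to stopping study drug: 0 of 3.

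**Step 3: does the study-discontinuation list fill the gap?** It has an Adverse Event row in both phases, so a subject who leaves the study for an adverse event is counted there. However:

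- The plan treats the two outcomes as distinct. The protocol gives them separate sections (5.3 and 5.3.1), and SAP 9.2 gives them separate completed/discontinued rows and separate reasons.
- The study row counts exits from the study. It gives the number of drug stops due to adverse events only if the two always coincide, which neither document states.
- It does not name the TEAE responsible.

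**Step 4: do the general listings fill it?** Listing 16.2.1.1 (disposition) and listing 16.2.7 (all adverse events) may hold individual reasons or the action taken. The SAP does not specify their columns, so this cannot be confirmed.

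**The case against.** The strongest reply is that little is lost in practice. Protocol 5.3 makes a serious or clinically significant adverse event a ground for ending participation. After an early drug stop, the protocol asks for the end-of-treatment assessments and sets out no separate off-drug visit schedule. The missing-data rule in SAP 11.1.1 speaks of leaving the study and has no separate provision for stopping drug. Many subjects who stop for an adverse event may therefore also leave the study and appear in its Adverse Event row. Individual review is also feasible in a study of about 19 subjects. And Protocol 10.2.3 never promises a table of TEAEs leading to discontinuation, so no committed safety analysis has been dropped.

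Much of this stands. It limits the loss in the count to cases where stopping drug and leaving the study diverge, or where the study exit is recorded under another heading such as Withdrawal of Consent. It does not supply the events responsible, and it does not explain why the SAP list is narrower than the protocol section it draws on.

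Stronger readings are tempting, and the documents do not support them:

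- *That the table would report a zero rate of stops for adverse events.* The treatment list has no such row, so it reports no figure for them.
- *That adverse-event exits are visible nowhere.* Exits from the study for an adverse event are shown.
- *That all safety-related stops go to Other.* Excessive response at Level 1, arguably a safety stop, has its own row.
- *That one stop can be sized as one in 19.* That is the planned enrolment. SAP 9.2 uses the Safety Set of each phase as denominator, and the size of the Extension Safety Set is not given.

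**Conclusion.** The point holds as a reporting gap that should be closed. In both phases, 0 of the 5 treatment-discontinuation categories identify an adverse event, another general safety reason or a subject's request. No TEAE summary or dedicated TEAE listing covers events leading to discontinuation of study drug. So no planned summary gives the number of drug stops due to adverse events or the TEAEs behind them. This matters most for the Extension Phase, where safety and tolerability is the primary objective. For the Core Phase it affects how fully the secondary safety objective is reported.

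The number of subjects affected cannot be estimated from the documents. The conclusion assumes that the tables are produced as SAP 9.2 and 13.2 list them, and that stopping drug and leaving the study need not coincide, as the separate lists imply. The primary efficacy analysis and the sample size are not touched.

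**What to change.** In SAP 9.2, add two rows, adverse event or other safety reason and subject request, to the treatment-discontinuation reasons in both phases. This matches Protocol 5.3.1 and uses the reasons that section already requires to be collected.

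In SAP 13.2.1, add a row for TEAEs leading to discontinuation of study drug. If the CRF links a drug stop to a specific event, also add either the corresponding SOC and PT summary in 13.2.3 or a dedicated listing in SAP 14.

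The cost is a few extra outputs and possibly some recoding. The CRF is not part of the documents. If its categories mirror the present SAP list, reasons recorded as Other would have to be reclassified from the detail held. Protocol 5.3.1 describes a reason at subject level, and the investigator's assessments in Protocol 9.1.1 cover severity and causality only. The sponsor should therefore confirm that a link from stop to event exists before committing to the event-level output.

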## 10.2.1 Disposition, Demographics, and Baseline Characteristics

Subject disposition will be summarized for the Safety Population. In addition, the number of subjects screened, the number of subjects who failed screening, and the reasons for screen failure will be summarized. Demographic and Baseline characteristics will be summarized for the Safety Population. Medical history and concomitant medications will be coded using Medical Dictionary for Regulatory Activities (MedDRA) and WHODrug dictionaries and summarized for the Safety Population.

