7.2 Full Analysis Set (FAS)

The Core Phase FAS will include all subjects who are enrolled into the study and gave informed consent.

The Extension Phase FAS will include all subjects who enter the Extension Phase.

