7.4 Safety Set (SAF)

The Core Phase Safety Set will include all subjects who receive at least 1 dose of study drug and have a post-dose safety assessment. The Extension Phase Safety Set will include all subjects who receive at least 1 dose of study drug in the Extension Phase and have a post-dose safety assessment in the Extension Phase. General Issues for Statistical Analysis.

8 General Issues for Statistical Analysis

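### Disposition is summarised on the Safety Set, so the Extension rows for entered, treated and not treated are fixed by definition, and any subject in the FAS but not the Safety Set drops out of the attrition summary

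*SAP*

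**What the plan says.** SAP 9.2 gives one population for the disposition table in both phases: "Population: Safety Set". Its denominators are "The number of subjects in Safety Set of Core Phase" and, for the Extension, "The number of subjects in Safety Set of Extension Phase". The Extension item list includes subjects who entered the phase, subjects treated, and "Subjects who weren't treated with study drug".

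SAP 7.4 defines the Extension set: "The Extension Phase Safety Set will include all subjects who receive at least 1 dose of study drug in the Extension Phase", with the further condition of a safety assessment after dosing in that phase. The Core Phase Safety Set has the same two conditions.

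The SAP also defines sets without a dosing condition. In 7.2 the Core FAS holds all enrolled, consented subjects, and for the Extension: "The Extension Phase FAS will include all subjects who enter the Extension Phase".

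The SAP follows the protocol here. Protocol 10.2.1 states: "Subject disposition will be summarized for the Safety Population". Demographics and baseline characteristics (SAP 10.1) also use the Safety Set. Major protocol deviations (9.3), analysis datasets (9.4) and the disposition listing 16.2.1.1 use the FAS.

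**The concern.** A disposition table should account for everyone who came in and show where they went. When its population is restricted to subjects who were dosed and then assessed, it cannot report anyone who was not dosed, or anyone lost before an assessment. Yet the Extension table has a row for untreated subjects, so the authors meant to report them.

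At stake is the readability of attrition in a trial of about 19 subjects. The primary objective of the Extension is long-term safety and tolerability, and very early losses are part of that picture. In the Core Phase, the primary analysis is on the FAS, and missing counts are non-response. An enrolled subject with no platelet counts therefore contributes zero weeks to the primary mean, but may have no disposition outcome in 9.2 and no baseline summary in 10.1.

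**Working it through.** The plan states no figure on this point. The check is set logic on its definitions, followed by an illustration.

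**Inputs.** Population and denominators: SAP 9.2. Safety Set: SAP 7.4. FAS: SAP 7.2. Non-response rule: SAP 11.1.1. Planned size 19: SAP section 6. Monthly Extension visits with a 7-day window either side: Protocol 7.3.1 and Appendix B.

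**Extension Phase.** Let E be the subjects who enter, D those of E who are dosed in the phase, and S those of D who also have a later safety assessment. Then S lies within D, and D within E.

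- Entered, counted within S: all of S / S = 100%.
- Treated, counted within S: all of S / S = 100%.
- Not treated, counted within S: nobody in S is outside D, so 0 / S = 0%.

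The other possible reading counts rows from all entrants and keeps S as the denominator. That contradicts the stated population and can exceed 100%.

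**Illustration.** Assume, as an upper bound on numbers, that all 19 enter and 1 is never dosed, so E = 19 and D = S = 18.

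| Row | 9.2 as written | All entrants over S | Extension FAS |
|---|---|---|---|
| Entered | 18/18 = 100% | 19/18 = 105.6% | 19/19 = 100% |
| Treated | 18/18 = 100% | 18/18 = 100% | 18/19 = 94.7% |
| Not treated | 0/18 = 0% | 1/18 = 5.6% | 1/19 = 5.3% |

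Only the last column is coherent and informative.

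**Dosed but not assessed.** The first scheduled Extension visit is at Month 1, plus up to 7 days: about 30 + 7 = 37 days. Without an earlier visit, a subject could take drug for that long, be lost, and never join S.

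**Core Phase.** Assume 19 enrolled and 1 without a dose or without a later assessment, so FAS = 19 and Safety Set = 18. The enrolled row reads 18/18 = 100%. If that subject is the only one to leave, 9.2 shows 0/18 = 0% discontinued and no reason. On the FAS it would be 1/19 = 5.3% with a reason.

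**Where the missing subject can still be found.**

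- SAP 9.1 counts Core Phase subjects treated and not treated among those who consented. It gives reasons for screen failure, not reasons for leaving after enrolment, and has no Extension part.
- SAP 9.4 gives FAS and Safety Set sizes for both phases, so the gap can be counted.
- Listing 16.2.1.1 gives individual disposition for both phases on the Core FAS. Listings 16.2.4.4 (ITP history) and 16.2.6.2 (local platelet counts) also use the Core FAS. The demographics listing 16.2.4.1 uses the Safety Set.

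**The case against.** The strongest case against has four parts.

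1. **The gap may be empty.** The first dose is given by the study team at the site (Protocol 6.4.3), platelet results must be available before enrolment (4.2.1), and the next visit is Day 5 (4.3.2). SAP 9.1 defines enrolled as consented minus screen failures and allows subject withdrawal as a screen-failure reason, so some pre-dose withdrawals never reach the FAS. This stands for the Core Phase. The Extension gap is also narrowed: dose adjustment, concomitant ITP medication reduction or rescue therapy triggers three weekly visits (Protocol 4.4), and early withdrawal calls for every effort to complete the end-of-treatment assessments (5.3). It does not rescue the Extension rows, which are fixed whatever happens.

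2. **The subjects are not lost from the report.** With about 19 subjects the listings can be read line by line. This stands as mitigation. However, 9.1 and 9.4 give counts without discontinuation reasons, and a summary table should cover the same subjects as its own listing.

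3. **The SAP follows the protocol.** It does, so this is a weakness shared by both documents and not a departure of one from the other.

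4. **Nothing inferential turns on it.** Correct. A reader might infer that the disposition population distorts the primary mean: with 1 undosed subject in 19 and the others averaging the assumed 12.0 weeks, the mean becomes 12.0 x 18/19 = 11.37. That drop comes from the non-response rule in SAP 11.1.1 and is the same whichever population 9.2 uses.

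**Conclusion.** The point holds as a reporting defect. Three Extension rows are predetermined, and any subject in the FAS but outside the Safety Set has no completion status or reason in 9.2 and no baseline summary in 10.1. Each such subject amounts to 1/19 = 5.3 percentage points of attrition at the planned size. The size is zero if every enrolled or entering subject is dosed and assessed. The 19-subject examples are assumptions; the fixed Extension rows follow from the definitions alone.

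Three stronger readings are not supported:

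- A reader might infer that everyone scoring zero weeks in the primary analysis is missing from disposition. Treated and assessed non-responders are in the Safety Set and do appear.
- A reader might infer that the Core Phase not-treated count is also forced to zero. That count is in 9.1, on consented subjects, and is free to vary. The fixed row is in the Extension table, whereas the primary endpoint is a Core Phase measure.
- A reader might infer that the Safety Set itself must be redefined. Repairing 9.2 does not need that, and it would alter a protocol definition on which the safety tables rest.

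**What to change.** In SAP 9.2, replace the Safety Set with the Core Phase FAS (all enrolled) for the Core table and the Extension Phase FAS (all who enter) for the Extension table, both as population and as denominator. Both sets are already defined in 7.2, and the table would then cover the same subjects as Listing 16.2.1.1.

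In SAP 10.1, keep the Safety Set summary and add an FAS column if the FAS and Safety Set differ.

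In SAP 5.1, declare the change from protocol 10.2.1. Leave the Safety Set definition as it is.

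The cost is SAP wording and possibly one extra table column. No new data are needed, and the primary analysis, its confidence interval and the sample size are unchanged. The SAP is to be finalised before the Core Phase database lock, so the change belongs before that point.
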